 - i. if Gilbert's Syndrome, with direct bilirubin within ULN.
- b. HbA1c $\leq 9.5\%$
- c. Platelet count $\geq 120,000/\text{mm}^3$

Subjects who meet the Baveno VI criteria with a platelet count $>110,000/\text{mm}^3$ and $<120,000/\text{mm}^3$ may be enrolled if they meet the expanded Baveno VI criteria. (Note: No more than 30% of the remaining population will be enrolled using the Baveno VI criteria.)

- d. Creatinine clearance ≥ 60 mL/min as calculated by Cockcroft-Gault equation
- e. Serum alanine amino transferase (ALT) levels $\leq 5 \times \text{ULN}$
- f. Serum aspartate amino transferase (AST) levels $\leq 5 \times \text{ULN}$
- g. Alkaline phosphatase $\leq 1.5 \times \text{ULN}$
- h. Serum albumin ≥ 3.5 g/dL
- i. International normalized ratio (INR) ≤ 1.7 .

Note: A 10% laboratory variability is allowed on platelets and bilirubin values.
Platelet variability does not apply to Baveno VI.

11. Female subjects must be either of a) non-childbearing potential, defined as women who have had a hysterectomy, bilateral oophorectomy, medically documented ovarian failure, documented postmenopausal, or a follicle stimulating hormone ≥ 40 mIU/mL, OR b) if of childbearing potential, defined as including women <55 years of age with ≤ 2 years of amenorrhea (absence of menstruation and not due to any reversible medical cause or any current medication use), then have a negative serum pregnancy test at Screening and urine pregnancy test at the Day 1 visit prior to first dose of study drug, and must be non-lactating and non-breastfeeding. Note: Females who do not meet this criterion can be included if they meet Inclusion Criterion 12.

12. Female subjects of childbearing potential and male subjects with a female partner of childbearing potential must agree to consistent and adequate birth control from Screening to EOS (Week 54):

- Recommended forms of contraception for males: condom, vasectomy, and sexual abstinence
 - i. Vasectomized partner is a highly effective birth control method provided that the partner is the sole sexual partner of the female subject of childbearing potential trial participant and that the vasectomized partner has received medical assessment of the surgical success.

- ii. Condom use is not considered as a highly effective form of contraception alone and may be used effectively with a second method of contraception.

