5.2. Exclusion Criteria

The following will exclude potential subjects from participating the study:

1. Other causes of liver disease that are primary, secondary, or otherwise causes of cirrhosis or which may confound the intended patient population according to the investigator, including but not limited to alcoholic liver disease, hepatitis B, hepatitis C, autoimmune disorders, primary biliary cirrhosis, drug-induced hepatotoxicity, Wilson's disease, hemochromatosis, and alpha-1-anti-trypsin deficiency based on medical history and/or centralized read of liver histology.
2. Evidence of drug induced steatohepatitis secondary to amiodarone, corticosteroids, estrogens, methotrexate, tetracycline, or other medications known to cause hepatic steatosis.
3. History of hepatic decompensation, including variceal bleeding, ascites, or hepatic encephalopathy.
4. Prior or pending liver transplantation.
5. Child Pugh class B and C status.

6. Model of end stage liver disease (MELD) score >12.
7. Evidence of worsening liver disease (defined below) between screening visits (i.e., Day -56 and Day -42) including measures of AST, ALT, alkaline phosphatase (ALP) or total bilirubin (TBL):
 - a. For subjects with TBL, AST, ALT, or ALP baseline levels >ULN, the second assessment should not exceed an increase of 35% over the first assessment.
- Note: An unscheduled visit may be necessary to confirm eligibility if the difference exceeds the allowable percent difference. If performed, unscheduled visit results will be compared to the average of Day -56 and Day -42 results to determine eligibility. If liver function tests are repeated to verify eligibility criteria have been met, there must be a minimum of 14 days (2 weeks) between the Day -42 visit and any unscheduled visit.
8. History of porto-systemic shunt procedure.
9. No evidence of gastroesophageal varices as documented by one of the following assessments:
 - a. A historical and locally evaluated EGD obtained within 365 days of screening or
 - b. A locally evaluated EGD conducted during the screening period

* If no EGD is available, the latest EGD assessment guidelines during a global pandemic† for patients with compensated cirrhosis (i.e., the expanded Baveno VI criteria, [Petta 2018](#)) as follows can be used as a replacement for the EGD to determine eligibility:

 - c. Platelet count >110,000/mm³, and a FibroScan® <30 kPa on a M probe or <25 kPa on a XL probe

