7.2. Discontinuation of Subjects from Study Participation

Subjects will be informed that they are free to withdraw from the study at any time and for any reason. The PI may remove a subject from the study if, in the PI's opinion, it is not in the best interest of the subject to continue the study. Subjects may be discontinued due to a change in compliance with an inclusion/exclusion criterion that is clinically relevant and affects subject safety, occurrence of AEs, occurrence of pregnancy, or administration of non-permitted concomitant medication that might affect subject safety or study assessments/objectives. In addition, for any AEs noted, the PI will determine whether there is impact, or a potential for impact, on subject safety or study assessments/objectives, and will remove such subjects. Subjects will be discontinued due to clinically relevant changes in a subject's status related to Inclusion and Exclusion criteria that significantly affect subject safety or study integrity, development of pregnancy, or necessary administration of non-permitted concomitant medications that might affect subject safety or study assessments/objectives. Notification of discontinuation will be made immediately to the sponsor Medical Monitor or designee. In case of premature discontinuation of study participation, efforts will be made to perform all final EOT and EOS visits/assessments. The date the subject is withdrawn from the study and the reason for discontinuation will be recorded on the subject's Case Report Form (CRF). All withdrawn subjects will be followed until resolution of any AEs or until any unresolved AEs are judged by the PI to have stabilized.

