^[h] All subjects are required to have a liver biopsy result at Screening and additional liver biopsy at Week 48. A Screening liver biopsy will be performed only in subjects who do not have a qualified historical biopsy available for central pathology evaluation. The Week 48 biopsy should be obtained before the last dose of aldafermin with a visit window of 7 days prior to the end of treatment period.

^[i] Adverse events will be monitored and recorded from subject signing informed consent through follow-up.

^[j] Serum chemistry will include ALT, AST, ALP, bicarbonate, bilirubin (direct and total), BUN, calcium, chloride, creatinine, CK, GGT, glucose, HDL, LDL, phosphate, potassium, proteins (albumin, total protein), sodium, total cholesterol, and TG. Lab results for ALT, AST, total cholesterol, LDL, HDL, and triglycerides are blinded to the site and sponsor from Week 2 onward.

[k] Creatine kinase will be collected at all time points as serum chemistry.

[l] Per Exclusion #7, total bilirubin, AST, ALT, ALP

[m] A serum pregnancy test will be performed on all female subjects of childbearing potential at Day -56 Screening visit, Week 24, and Week 48. A urine pregnancy test will be performed on all female subjects of childbearing potential at all study visits through EOS.

[n] Urine drug and alcohol tests may be repeated during treatment for subjects suspected of excessive alcohol intake or to rule out association with a safety event.

[o] Serum bile acids will be collected pre-dose Day 1 and Week 48/early withdrawal.

[p] C4 will be collected pre-dose on Day 1 and Weeks 2, 6, 12, 18, 24, 30, 36, 42, 48 and 4-h post dose on Days 1, Weeks 24, and 48. In addition, for subjects participating in the optional PK sub-study, additional C4 will be tested at the same time points as the PK blood sample collections: Day 1 and Week 48 at pre-dose, and post-dose at 0.5, 1, 2, 4, 6, 8, 12, and 24 hours. The window for sample collection for the pre-dose through 4 hours is ± 5 minutes, 6-12-hour time points is ± 30 minutes. The window for sample collection for the 24-hour time points is -2 hours.

[q] PK blood samples will be collected in all subjects before dosing themselves in the clinic (pre-dose) on Day 1, Weeks 2, 6, 12, 18, 24, 30, 36, 42, and 48 and 4-hours post-dose on Day 1, Week 24 and Week 48.

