8.2.3. Day 1 Procedures

Subjects will report to clinic fasted. The following procedures will be performed at the Day 1 Visit:

Pre-dose:

- Reassess inclusion/exclusion criteria
- Measure body weight, BMI, and waist circumference
- Conduct physical examination and RUQ pain assessment with NRS
- Obtain 12-lead ECG (after subject has been supine for at least 5 minutes)
- Measure vital signs (including temperature, respiratory rate, and seated blood pressure and pulse)
- Record concomitant medications
- Record new and/or changes to AEs
- Obtain 10-hour fasted clinical laboratory samples for the following:

- Chemistry, including creatine kinase.
- CBC
- HbA1c
- [REDACTED]
- Insulin level
- HOMA-IR calculation
- INR
- Lipid panel
- Lipoprotein particles
- Lipase
- C4
- Serum bile acids
- PK
- Anti-drug antibodies (ADAs)
- Neutralizing antibodies (NAbs)
- ELF panel
- Pro-C3
- Pro-C3X
- CTX-III
- C3M
- Exploratory Plasma biomarker #1
- Exploratory Plasma biomarker #2
- Exploratory Serum biomarker #3
- Single exploratory buccal swab sample for PNPLA3/other genetic biomarkers
- Obtain urine sample for:
 - Pre-dose urine pregnancy in all female subjects of childbearing potential
 - Urinalysis
 - Urine drug screen
- Randomize subject [REDACTED]

In-clinic dosing and post-dose assessments/activities:

- Dispense initial aldafermin study drug kit and home diary
- Provide aldafermin study drug self-administration training
- Oversee subject's aldafermin study drug self-administration

- Perform local injection site symptom assessment (LISSA) evaluation.
- Obtain PK blood sample [REDACTED]
- C4 blood sample [REDACTED]

Before clinic discharge:

- Remind subject to bring study drug kit and diary at the next clinic visit and not to self-administer aldafermin/placebo at home on clinic visit days
- Schedule Week 2 visit

[REDACTED]

[REDACTED]

[REDACTED]

[REDACTED]

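### As worded, the note to Inclusion Criterion 11 lets a contraception agreement stand in for the negative pregnancy tests and the non-lactating condition at entry

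*Protocol*

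**What the plan says.** Criterion 11 (protocol, Section 5.1, and the same criterion in the synopsis) has two limbs. Limb 11a covers women of non-childbearing potential, by a list of qualifying grounds. Limb 11b covers women of childbearing potential, described as including those under 55 with no more than two years of amenorrhea. It requires a negative serum test at Screening, a negative urine test on Day 1 before the first dose, "and must be non-lactating and non-breastfeeding". The criterion ends with the note: "Females who do not meet this criterion can be included if they meet Inclusion Criterion 12".

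Criterion 12 reads: "Female subjects of childbearing potential and male subjects with a female partner of childbearing potential must agree to consistent and adequate birth control". The rest of it lists contraceptive methods. It contains no pregnancy test and no lactation condition.

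Three other places bear on the point. Footnote m of Table 8 (Section 8.1) schedules serum tests at Day -56, Week 24 and Week 48, and adds: "A urine pregnancy test will be performed on all female subjects of childbearing potential at all study visits through EOS". Section 8.2.3 lists among the Day 1 pre-dose procedures, ahead of randomization: "Pre-dose urine pregnancy in all female subjects of childbearing potential". Section 7.2 names among the reasons for which subjects will be discontinued: "development of pregnancy, or necessary administration of non-permitted concomitant medications that might affect subject safety".

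**The concern.** The note has no stated scope. It refers to the whole of Criterion 11, so it reaches the test and lactation requirements of 11b as well as the definitions of childbearing status. A woman of childbearing potential whose status is clear, but who fails 11b because of a positive test or because she is lactating, does not meet the criterion. The note then admits her if she agrees to contraception.

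At stake is an entry safeguard, not the analysis. If 11b can be bypassed, enrolling such a woman would comply with the protocol and would not count as a deviation. The primary endpoint, the sample size and the analysis are unaffected.

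**Working it through.** No arithmetic applies, so the check is one of logic and of setting the passages side by side.

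**1. What the criteria require with and without the note.** All inclusion criteria must be met, and Criterion 12 already binds every female subject of childbearing potential.
- Without the note, such a woman must satisfy 11b and 12.
- With the note, she must satisfy (11b or 12) and 12. This reduces to 12 alone.

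For this group, then, the note's only effect is to remove 11b as a condition of entry.

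**2. Who is affected.**

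| Woman | Without the note | With the note as written |
|---|---|---|
| Meets 11a | meets Criterion 11 | no change |
| Childbearing potential, tests negative, not lactating | meets Criterion 11 | no change |
| Childbearing potential, positive test | fails | admitted if she meets 12 |
| Childbearing potential, lactating or breastfeeding | fails | admitted if she meets 12 |
| Status fits neither 11a nor the age and amenorrhea wording of 11b | unclear or fails | admitted if she meets 12 |

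The third and fourth rows are the defect. The last row is the group for which the note was plausibly written.

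**3. Whether anything else restores the condition.**
- *Exclusion criteria (Section 5.2, 1 to 26).* None names pregnancy or lactation. Criterion 21b cites the rosuvastatin package insert, but only for contraindicated medications and hypersensitivity. Criterion 26 is a general clause left to the investigator's opinion.
- *Table 8, footnote m.* The tests are scheduled, but the footnote attaches no eligibility consequence to the result.
- *Section 8.2.3.* The urine test is done before dosing, and the inclusion and exclusion criteria are reassessed on Day 1. The criteria reassessed include the note.
- *Section 7.2.* Discontinuation for pregnancy acts on subjects already in the study. It does not mention lactation.

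For pregnancy, several provisions point the same way, but none sets an entry condition on the test result. For lactation, 11b is the only place in the protocol that sets any condition, and it is the limb that the note waives.

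**The case against.** The strongest reply is that the note has a sensible purpose. Some women fall outside both limbs: for example, a woman of 55 or over whose menopause is not documented, or one under 55 with more than two years of amenorrhea and none of the grounds listed in 11a. Sending them to Criterion 12 treats them as being of childbearing potential. Read with the obligatory wording of 11b, the scheduled tests, the Day 1 reassessment and Section 7.2, the note was hardly meant to admit a woman with a positive test. Knowingly enrolling one would run against the protocol's own discontinuation rule, and an investigator could also invoke Exclusion 26.

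Most of this stands. It is good evidence of intent, it lowers the practical risk for pregnancy, and it is a reason not to strike the note altogether. It does not cure the text. The note does not confine itself to the neither-limb group, and Exclusion 26 is discretionary. The reply also offers nothing specific on lactation.

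A reader might infer that the waiver reaches every woman of childbearing potential who agrees to contraception. That is too wide: a woman who satisfies 11b needs no waiver, so the outcome changes only for those with a positive test or who are lactating. A reader might also infer that the protocol means to enrol pregnant women. The testing schedule and Section 7.2 speak against that.

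**Conclusion.** The point holds as a defect of wording in an entry safeguard. As written, the note waives the only entry conditions on pregnancy-test results and lactation. The waiver bites for women of childbearing potential who test positive, lactate or breastfeed; how many would present at screening cannot be estimated from the protocol. The practical risk is reduced for pregnancy, and the gap that no other provision addresses is lactation. The conclusion rests on a literal reading of the note; the likely intent was narrower. It should be fixed, because the correction restores the protocol's own rule at almost no cost.

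A reader might infer that the retest note under Exclusion 7 undoes its criterion in the same way, since "unscheduled visit results will be compared to the average of Day -56 and Day -42 results to determine eligibility" and that average contains the value that prompted the retest. The documents do not support treating it as a parallel defect. The averaged comparator is stated consistently in the synopsis, Section 5.2 and Section 8.3.8. The 35% in 7a is the only percentage in the criterion and carries over naturally, and Section 8.1 names no competing comparator. At most that text could be clarified.

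**What to change.** In Section 5.1 and the synopsis, limit the note to women whose childbearing status fits neither 11a nor the age and amenorrhea wording of 11b. State there that it does not waive the negative-pregnancy-test and the non-lactating and non-breastfeeding requirements already in 11b. Do not simply delete the note, because that could shut out the neither-limb women it seems meant to serve.

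The cost is a wording change in two places. It needs no new tests or visits and no change to sample size or analysis.

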5.2. Exclusion Criteria

The following will exclude potential subjects from participating the study:

1. Other causes of liver disease that are primary, secondary, or otherwise causes of cirrhosis or which may confound the intended patient population according to the investigator, including but not limited to alcoholic liver disease, hepatitis B, hepatitis C, autoimmune disorders, primary biliary cirrhosis, drug-induced hepatotoxicity, Wilson's disease, hemochromatosis, and alpha-1-anti-trypsin deficiency based on medical history and/or centralized read of liver histology.
2. Evidence of drug induced steatohepatitis secondary to amiodarone, corticosteroids, estrogens, methotrexate, tetracycline, or other medications known to cause hepatic steatosis.
3. History of hepatic decompensation, including variceal bleeding, ascites, or hepatic encephalopathy.
4. Prior or pending liver transplantation.
5. Child Pugh class B and C status.

6. Model of end stage liver disease (MELD) score >12.
7. Evidence of worsening liver disease (defined below) between screening visits (i.e., Day -56 and Day -42) including measures of AST, ALT, alkaline phosphatase (ALP) or total bilirubin (TBL):
 - a. For subjects with TBL, AST, ALT, or ALP baseline levels >ULN, the second assessment should not exceed an increase of 35% over the first assessment.
- Note: An unscheduled visit may be necessary to confirm eligibility if the difference exceeds the allowable percent difference. If performed, unscheduled visit results will be compared to the average of Day -56 and Day -42 results to determine eligibility. If liver function tests are repeated to verify eligibility criteria have been met, there must be a minimum of 14 days (2 weeks) between the Day -42 visit and any unscheduled visit.
8. History of porto-systemic shunt procedure.
9. No evidence of gastroesophageal varices as documented by one of the following assessments:
 - a. A historical and locally evaluated EGD obtained within 365 days of screening or
 - b. A locally evaluated EGD conducted during the screening period

* If no EGD is available, the latest EGD assessment guidelines during a global pandemic† for patients with compensated cirrhosis (i.e., the expanded Baveno VI criteria, [Petta 2018](#)) as follows can be used as a replacement for the EGD to determine eligibility:

 - c. Platelet count >110,000/mm³, and a FibroScan® <30 kPa on a M probe or <25 kPa on a XL probe

Note: No more than 30% of the remaining population will be enrolled with the expanded Baveno VI criteria.

† *EGD waived in patients with compensated cirrhosis during a global pandemic per AASLD/ASGE guidelines.*
10. Clinically significant cardiovascular or cerebrovascular event or new diagnosis within 6 months of Screening, including but not limited to congestive heart failure, myocardial infarction, acute coronary syndrome, revascularization, stroke (hemorrhagic or ischemic), transient ischemic attack (TIA), or implanted defibrillator or pacemaker (for uncomplicated elective, non-biventricular pacemaker procedure, 3 months post procedure will be allowed).
11. Gastric bypass or bariatric surgery in the past 5 years or planned procedure during the study period.
12. History of clinically significant unstable or untreated illness or any other major medical disorder that may interfere with subject treatment, assessment, or compliance with the protocol.
13. Documented significant weight change ($\pm 5\%$) <3 months prior to Screening.

14. Screening ECG with clinically significant abnormalities that in the investigator's opinion, require evaluation and possible treatment.
15. Positive for HBsAg, antiHIV Ab, or antiHCV Ab plus HCV-RNA. Subjects who are antiHCV Ab- positive but HCV-RNA negative (secondary to treatment or viral clearance) are eligible with at least a 1-year period since documented sustained viral response at Week 12 post-treatment.
16. History of malignancy diagnosed or treated within 2 years (recent localized treatment of squamous or non-invasive basal cell skin cancers is permitted; cervical carcinoma *in situ* or breast ductular carcinoma *in situ* is allowed if appropriately treated within 2 years prior to Screening); subjects under evaluation for suspected malignancy are not eligible. History of hepatocellular carcinoma at any point regardless of treatment or treatment success will be excluded.
17. A positive drug screen (e.g., morphine, heroin, cocaine) will exclude subjects unless it can be clearly explained by a prescribed medication. The diagnosis and prescription must be approved by the investigator and the Medical Monitor.
18. Significant alcohol intake as measured by a phosphatidylethanol (PEth) level ≥ 200 ng/mL AND significant alcohol use, as determined by the Alcohol Use Disorders Identification Test (AUDIT-C) alcohol consumption questionnaire ([Appendix 3](#)).

19. Criterion deleted per protocol Version 3.0.

20. Consumption of ≥ 21 units of alcohol per week in males and ≥ 14 units of alcohol per week in females for two years prior to screening, where a "unit" of alcohol is equivalent to a 12-ounce beer, 4-ounce glass of wine, or 1-ounce shot of hard liquor.
21. Use of any prohibited concomitant medications as described in [Section 6.4](#) within 3 months prior to screening;
 - a. Weight loss medications.
 - b. Any medication that is contraindicated according to the rosuvastatin package insert ([Appendix 5](#)) or if subject has a known hypersensitivity to rosuvastatin product components ([Section 6.1.3](#)).
 - c. Hepatotoxic medications ([Appendix 6](#)); allopurinol allowed.
 - d. Anabolic steroids.
22. History of statin intolerance, as defined by presence of significant side effects while on statins and/or inability to take or use statins for treatment.
23. Prior participation in a clinical trial of aldafermin unless previously enrolled into a placebo arm of the trial.
24. History of severe allergic or anaphylactic reactions to recombinant therapeutic proteins, fusion proteins, or chimeric, human, or humanized antibodies.

25. Participation in a study of another investigational agent within 28 days or five half-lives of the drug (whichever is longer) prior to Screening.
26. Any acute or chronic condition that, in the opinion of the investigator, would limit the subject's ability to participate, complete, and/or would confound data interpretation in this clinical study.

